
### Data Analysis

The main hypothesis to be tested is that participants in the intervention group will have higher medication adherence and significantly greater improvement in A1c, blood pressure, LDL-cholesterol, and measures of quality of life; and fewer barriers to adherence compared to control patients. While medication adherence can be considered as a continuous variable, we will follow the literature and treat adherence as a binary outcome by classifying participants as non-adherent if measured adherence is <80% and adherent otherwise. Therefore, unadjusted testing of the main hypothesis will use two-sided  $X^2$  tests and statistical modeling will use logistic

regression. The other primary outcomes (A1c, blood pressure, LDL-cholesterol) and the secondary study outcomes of physical and mental functioning, as measured by the SF-12, diabetes distress, and barriers to adherence are all continuous or ordinal measures. As such unadjusted hypothesis tests for these outcomes will use t-tests or the Wilcoxon-Mann-Whitney test, as appropriate, and statistical modeling will use linear regression. Analysis will begin by calculating ICCs for each outcome to assess the magnitude of clustering; if the ICCs are found to be significantly non-zero with  $p < 0.05$  or with a point estimate greater than 0.01, testing of main hypotheses will use unadjusted regression models (logistic or linear, as appropriate) with Generalized Estimating Equations (GEE) to account for clustering. All regression models for outcomes with non-negligible ICCs will use GEE to account for clustering due to randomization at the town level, and will be repeated using mixed models treating the towns as random effects with results examined for consistency.

The primary analysis will test the hypothesis that medication adherence treated as a binary outcome will be greater in the treatment arm than the control arm at follow-up. As above, the primary unadjusted hypothesis test will use either a  $X^2$  test or logistic regression with GEE depending on the magnitude of observed ICCs. Statistical significance will be judged by  $p < 0.05$  for either the  $X^2$  test or the coefficient for study group in regression models. The intervention group will be compared to the control group; further analyses will use logistic regression with GEE to model adjusting for any covariates that were imbalanced between groups at baseline, and will then proceed to examine regression models adjusted for the covariates described in Table 6.

Analysis for A1c, blood pressure and LDL-cholesterol and the secondary outcomes will be very similar to the analysis of medication adherence described above. We note that we will also be able to analyze adherence as a continuous outcome as a secondary analysis using the following approach. For each of these continuous or ordinal measures, we will begin by calculating the change from baseline to 6-month follow-up for each participant. These change scores will be the units of analysis and we hypothesize greater change among the intervention groups compared to the control group. We will proceed to examine summary statistics, histograms, and scatter plots of the measured outcomes for outliers and data trends. We will then test for unadjusted differences in changes between the intervention and control groups using t-tests, Mann-Whitney-Wilcoxon tests, or regression models with GEE to account for clustering, as appropriate for the variable and ICC. Similar to above, we will then proceed with more sophisticated analyses in stages, first adjusting for baseline values of outcome variables, then for any factors that were imbalanced at baseline and finally adjusting for covariates mentioned above.

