**Aim 2:** Conduct a randomized controlled trial with 500 individuals with type 2 diabetes and medication nonadherence. The trial will compare the effect of usual care and the intervention on medication adherence and physiologic risk factors including A1c, blood pressure and low density lipoprotein cholesterol (primary outcomes), and quality of life and self-efficacy (secondary outcomes).

This innovative approach would be a major shift in how we help patients in under resourced areas living with chronic diseases commit to taking medications, improving health and eventually reducing health disparities.

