## Study Design

We will compare usual care to viewing an educational DVD including peer storytelling and a 6-month telephone-delivered peer coaching intervention. We propose to use an RCT design because we aim to test the effectiveness of the intervention on medication adherence and A1c, blood pressure and cholesterol.

The trial will be cluster-randomized to reflect the clustering of patients within tightly knit small rural communities. People talk frequently within these communities, and if two participants from the same town are in different trial arms and compare notes, this could change their behavior and threaten the validity of the study. Each of the anticipated 80-100 towns will therefore be group-randomized in blocks to avoid contamination across trial arms. We considered using physician practices as clusters, but we have learned that it is common for different family members to attend different practices many miles from home.

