## Randomization

We will use a block randomization scheme for randomization. The units of randomization are towns identified by zip codes. We will group towns by size (small and not small) within each of the 4 regions, resulting in 8 strata. We will balance the strata so that at least 3 towns are in each stratum. With 55 towns in the two regions participating in the 400-member Encourage study, we conservatively estimate at 80-100 towns with the addition of two more regions, providing sufficient sample as well as clusters

As participants agree to enroll and provide informed consent, they will be randomized as a representative of their town. That is, the first member of a given town will determine the randomization status of that town. All subsequent town residents will be placed into the same trial arm as the first participant from that town. Informed consent will be obtained from all participants. We will obtain verbal consent over the telephone at the time of the baseline telephone interview. Formal written informed consent will be obtained at the time of the in-home data collection visit. Participants will view a video providing information about the study with the opportunity to call a toll-free number for questions.

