### Power Calculations and Sample Size

This study is powered to detect clinically meaningful differences in changes in medication adherence, A1c, blood pressure and LDL-cholesterol between either of the intervention arms compared with the usual care arm. The secondary outcomes are based on surveys (disease acceptance, quality of life). To consider the clustering of patients within town, we used a variance inflation factor  $D = [1 + \rho(m - 1)]$ , where  $m$  is the number of participants per community and  $\rho$  is the intra-class correlation (ICC). We conservatively estimate that we will have at least 80 clusters, corresponding to an average of 6-8 participants per cluster, with ICC=0.01 and 0.05 yielding  $D=1.084$  and  $1.419$ , respectively. Dividing the sample size per group  $N$  by  $D$  gives  $N_{\text{EFF}}$ , the effective sample size. In the Encourage study, those reporting nonadherence at baseline demonstrated ICCs in the range of 0.001-0.015 for most measures. To be conservative because we include new communities, we present power calculations for ICC=0.01-0.05. We observed 20% attrition over one year in the Encourage study and although attrition is likely to be lower over 6 months, we assume 20% attrition here, leaving 200 participants per group. Table 7 displays the detectable differences in adherence proportions and the difference in mean changes between groups detectable with 80% power using 2-sided  $X^2$  and t-tests with  $\alpha=0.05$ . We used variances based on the Encourage sample reporting nonadherence at baseline. We hypothesize that the intervention will result in improved medication adherence. Because eligibility requires low adherence at baseline, we expect low acceptance at baseline. Starting with low baseline values by design eliminates ceiling effects and allows us to reasonably anticipate large changes in the intervention groups and only modest changes in the control arm, as was seen in a storytelling intervention directed at blood pressure. For  $N=200$  per group, the difference in rates of medication adherence treated as a binary outcome detectable with 80% power depends on the proportion observed in the intervention group. If adherence is only 20% in the intervention group, then we can detect as different rates among the control group of 8.8-10.1%, depending on ICC. These rates are both lower than we anticipate for the intervention group and considerably higher than we expect in the control group. Assuming 200 participants per group we will have 80% power using 2-sided t-tests to detect differences of 0.28-0.32 standard deviations for continuous outcomes. Using variance estimates from Encourage data for change in the Diabetes Distress Score, another validated psychometric instrument, this translates into detecting differences as small as 3.7-4.4% of the range. Similarly, detectable differences for change in A1c are in a clinically meaningful range from 0.41-0.48%. We anticipate detectable differences for systolic blood pressure of 3-4 mmHg, and for LDL-cholesterol of 6.7-8.1 mg/dL.

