8. Are you willing to work with 5-7 clients over 5 months, by telephone, at first weekly, and then biweekly and monthly?	 Yes  No																												
9. Are you willing to attend weekly group phone calls with other peer advisors and study doctors?	 Yes  No																												
10. For every client you take on, you will need to spend about 1 hour a week scheduling calls, completing the program, and completing paperwork. This will be weekly for the first 2 months and then biweekly and monthly for the last 3 months. Most peer advisors choose to take 3-5 clients at a time. In addition to your client calls, you will generally have 2 meetings every week or every 2 weeks. Both meetings together will last 30 minutes. You will meet with UAB staff one-on-one for about 30 minutes per week. On a scale from 1 to 10, 1 being not confident at all to 10 being very confident, how confident are you that you will have enough time for the project?	
 
 not confident		very confident	
 
 1	2	3	4	5	6	7	8	9	10		
 
	not confident										very confident			1	2	3	4	5	6	7	8	9	10					
not confident										very confident																			
1	2	3	4	5	6	7	8	9	10																				
11. On a scale from 1 to 10, 1 being not easy and 10 being very easy, how easy is it for you to listen to other people?	
 
 not easy		very easy	
 
 1	2	3	4	5	6	7	8	9	10		
 
	not easy										very easy					1	2	3	4	5	6	7	8	9	10			
not easy										very easy																			
1	2	3	4	5	6	7	8	9	10																				

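### Whether the primary test allows for town randomisation is left to an observed ICC that about 80 small towns estimate too imprecisely to decide it

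*Combined protocol and SAP*

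**What the plan says.** The Randomization section states: "The units of randomization are towns identified by zip codes". The Study Design section gives the reason: "The trial will be cluster-randomized to reflect the clustering of patients within tightly knit small rural communities". The Power Calculations and Sample Size section allows for this with D = 1 + ρ(m − 1) at ICCs of 0.01 and 0.05, and reports ICCs of 0.001-0.015 for most measures in the earlier Encourage study.

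The Data Analysis section calculates an ICC for each outcome first. If that ICC has p < 0.05 "or with a point estimate greater than 0.01, testing of main hypotheses will use unadjusted regression models (logistic or linear, as appropriate", the sentence then adds that these models use GEE. That is the branch that keeps the clustering; the problem is its complement. The complement is plainest in the paragraph on the primary analysis, where the unadjusted adherence test is a chi-square "test or logistic regression with GEE depending on the magnitude of observed ICCs", and p < 0.05 from whichever is used counts as significant. The change-score comparisons for A1c, blood pressure, LDL-cholesterol and the secondary outcomes follow the same rule, with t or Wilcoxon tests in place of chi-square.

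GEE is named without the ICC condition only for the later covariate-adjusted adherence models. The mixed-model repeat is confined to outcomes whose ICC is judged non-negligible. Neither covers the primary test when the ICC estimate is 0.01 or less and not significant.

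**The concern.** In a town-randomised trial the clustered analysis follows from the design, not from the estimated ICC. A small or non-significant ICC is not evidence that clustering is absent, least of all when the estimate is imprecise. When the rule selects the unclustered test, about 400 participants are treated as independent and the standard error is too small if the true ICC is above zero. The rule also lets the data choose the primary test, so different primary outcomes could be tested by different methods. And it is at odds with the sample-size section, which deflates N for clustering that the analysis may then ignore.

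**Working it through.** **Inputs.** From Study Aims: "Conduct a randomized controlled trial with 500 individuals with type 2 diabetes and medication nonadherence". From Power Calculations and Sample Size: "at least 80 clusters, corresponding to an average of 6-8 participants per cluster" and "we assume 20% attrition here, leaving 200 participants per group". So 500/80 = 6.25 enrolled and 400/80 = 5 analysed per town. Tests are two-sided at 0.05.

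**The plan's design effect.** D = 1.084 at ICC 0.01 needs m = 1 + 0.084/0.01 = 9.4. D = 1.419 at ICC 0.05 needs m = 1 + 0.419/0.05 = 9.38. The stated 6-8 per town gives 1.05-1.07 and 1.25-1.35, so the printed D is not reproduced from the stated cluster size. That is a separate matter; both cluster sizes are carried below.

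**Cost of ignoring clustering.** The unclustered SE is too small by 1 − 1/√D, and its false-positive rate is 2[1 − Φ(1.96/√D)].

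| Setting | D | SE too small by | False-positive rate |
|---|---|---|---|
| m = 5, ICC 0.01 | 1.04 | 1.9% | 5.5% |
| m = 5, ICC 0.05 | 1.20 | 8.7% | 7.4% |
| Plan's D, ICC 0.01 | 1.084 | 4.0% | 6.0% |
| Plan's D, ICC 0.05 | 1.419 | 16% | 10.0% |

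**Precision of the ICC estimate.** SE ≈ (1 − ρ)[1 + (m − 1)ρ]√{2/[m(m − 1)(k − 1)]} with k = 80 and m = 5. At ρ = 0 this is √[2/(5 × 4 × 79)] = 0.036. At ρ = 0.05 it is 0.95 × 1.20 × 0.036 = 0.041. The 0.01 cut is about a quarter of one SE, and the earlier study's ICCs lie on both sides of it.

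**Simulation of the rule.** 20,000 runs per scenario; 80 towns, 400 analysed; beta-binomial outcome with 20% adherence in both arms; ANOVA ICC with F test. Chi-square is used if the ICC is ≤ 0.01 and p ≥ 0.05; otherwise a cluster-robust test on K − 2 df, where K is the number of towns. Paired entries are equal town sizes / town-size CV 0.8.

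| True ICC | Clustering dropped | Error when dropped | Error of whole rule | Error if always clustered |
|---|---|---|---|---|
| 0 | 63% / 63% | 5.5% / 5.2% | 4.6% / 4.7% | 5.1% / 5.3% |
| 0.01 | 52% / 52% | 5.4% / 5.9% | 4.5% / 5.0% | 4.8% / 5.4% |
| 0.015 | 47% / 47% | 5.6% / 6.0% | 4.5% / 5.0% | 4.8% / 5.3% |
| 0.05 | 17% / 19% | 7.7% / 9.1% | 5.0% / 5.4% | 5.1% / 5.3% |

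Further runs with a town-size CV of 0 or 0.74, and with a continuous outcome or a 15% rate, widen these ranges slightly. At ICC 0.01-0.015 the error when dropped is 5.0-6.6%. At ICC 0.05 clustering is dropped in 17-21% of trials, with an error of 8.7%. The whole rule runs at 4.2-6.1%. With 43 towns of about 9.3, close to the m behind the printed D, clustering is dropped in 53% of trials at ICC 0.01 and 12% at 0.05, with errors of 6.4% and 10.0%.

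**Why the whole rule stays near 5%.** The GEE branch is selected for high between-town variance, so it rejects less often. With equal towns at ICC 0.01 its rate is (4.49 − 0.5169 × 5.37)/0.4831 = 3.5%, which offsets the other branch.

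**The case against.** The strongest reply is that the rule as a whole holds its level, at about 4-6% against 4.7-5.7% for always clustering. That stands. A reader might infer large overall inflation of the false-positive rate; the figures do not support it.

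A related point also stands. In the trials where clustering is dropped, a cluster-robust test would reject about as often as chi-square. With equal towns at ICC 0.05 its rate there is 7.74 + (5.08 − 5.04)/0.1732 = 8.0%, against 7.7%; at ICC 0.01 it is 5.37 + (4.80 − 4.49)/0.5169 = 6.0%, against 5.4%. An ICC that is low by chance shrinks the robust SE too. The argument for the change is therefore one prespecified test that matches the randomisation, not a lower error rate in that subset.

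The harm is also modest at the ICCs the sponsor has observed: 5.0-6.6% at 0.01-0.015. The 8-9% needs an ICC of 0.05, which the plan chose to be conservative.

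Other stronger readings fail:

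- The SE is not 19% too small under the plan's D. √1.419 = 1.191 means the correct SE is 19% larger, so the unclustered one is 16% too small.
- The ICC rule is not uninformative. It keeps clustering in 79-83% of trials at ICC 0.05 and in 37% at ICC 0. It discriminates, but poorly.
- The peer-advisor screening form asks "Are you willing to work with 5-7 clients over 5 months, by telephone", from which a reader might infer a second layer of clustering across towns. The documents do not say how advisors are matched across towns, and the Background describes coaches as living in the same community. To the extent that coaching stays within a town, town-level clustering absorbs it. It is not part of this point.

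**Conclusion.** The point holds. The plan allows an unclustered primary test in a town-randomised trial and makes that choice from an ICC estimate with an SE of about 0.04. The unclustered branch is likely: about half of trials at a true ICC of 0.01-0.015, and 17-21% at 0.05. Ignoring clustering makes the SE about 2-9% too small at 5 per town for ICCs of 0.01-0.05, or 4-16% under the plan's stated D. The false-positive rate in that branch is about 5.0-6.6% at ICC 0.01-0.015 and about 8-9% at 0.05. Averaged over both branches it is near 5%. The defect is therefore under-coverage when the unclustered test is used, together with a data-driven primary test.

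The 80 towns and 400 analysed participants come from the plan. The town-size variation, the adherence rate under the null, the beta-binomial model and the ICC estimator are assumptions of the simulation.

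**What to change.** Delete the ICC rule from the Data Analysis section, both where it is introduced and in the paragraphs on the primary adherence test and the change scores. For every primary and secondary outcome, prespecify a town-clustered test whatever the observed ICC:

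- GEE clustered on town with small-sample-corrected standard errors;
- the planned mixed model as the consistency check, also without the ICC condition;
- a cluster-adjusted rank or ordinal method where Wilcoxon was intended.

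Report ICCs descriptively only. The wording should be settled before outcome data are examined by arm.

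The cost is SAP text and a slightly larger critical value: t on 78 df is 1.991 against 1.966 on 398 df, and 1.991/1.966 = 1.013, so intervals are about 1% wider if the true ICC is zero. In the simulation, always clustering held the error at 4.8-5.5% over ICCs from 0 to 0.05.

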3. During this visit, we will also make a list of all medications the participant is currently taking.
4. Provide participant with health report card

After the completion of the in-person data collection, the participant will be given the materials for the program. If the participant is in the control condition, they will be given a general health education DVD. Participants in the intervention condition will be matched with their peer advisor and given an activity book that they will use during their sessions with their peer advisors. All participants will receive their portable DVD player at the end of the data collection visit. Participants will receive a Health Report Card that provides their a1c, LDL-cholesterol, blood pressure, and weight data. If needed, participant in the intervention arm will receive a study phone.

Participants will be asked by the research staff at the in person data collection visit if they would like to use a study phone. Study phones will be taken back at the 2nd in-person study visit. Copies of the consent, in-person data collection form, and Health report card are included in Appendix F.

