### How long would I be involved?

The Living Well with Diabetes study will last approximately 1 to 1.5 years.

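### Peer advisors may form clusters that cross towns in the intervention arm only; the plan allows for town at most, so the standard error of the arm difference can be too small

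*Combined protocol and SAP*

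**What the plan says.** Randomization is by town: "The units of randomization are towns identified by zip codes". Under Data Analysis, ICCs are calculated first. If an outcome's ICC is significant at 0.05 or its point estimate exceeds 0.01, regression "will use GEE to account for clustering due to randomization at the town level", and the models are repeated with town as a random effect. Otherwise the unadjusted test is a chi-square, t or Wilcoxon test. The design effect under Power Calculations and Sample Size also has a town term only.

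The intervention is telephone coaching. At the baseline visit, "Participants in the intervention condition will be matched with their peer advisor"; no matching rule follows. Appendix B asks candidate advisors, "Are you willing to work with 5-7 clients over 5 months, by telephone", says that most carry 3-5 clients at once, and asks for at least a year's service. It adds: "The Living Well with Diabetes study will last approximately 1 to 1.5 years". Control participants receive a general health DVD and no coach. The sections available (the first of two parts of the document) nowhere name the advisor as a cluster, random effect, covariate or sensitivity analysis.

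**The concern.** Clients of the same advisor share a source of variation that control participants do not have. A town-level GEE picks this up only between clients who live in the same town. If one advisor coaches people in several towns, those towns are correlated, yet both the GEE and the town random-effects model treat them as independent. The p-value for the arm contrast would then be somewhat too small, and a few unusually good or poor advisors could move the result without the confidence interval showing it.

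Several features make crossing likely. Intervention towns are small. Delivery is by telephone. The Peer Advisor Manual has client names passed on by the community coordinator or study staff. A town's arm is unknown until its first resident enrols, yet session 1 is due within 7 days of the advisor receiving a name. One ready, trained advisor per intervention town would be hard to arrange.

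**Working it through.** **1. The plan's own figures.** Analysed size reproduces: "Conduct a randomized controlled trial with 500 individuals with type 2 diabetes" and "we assume 20% attrition here, leaving 200 participants per group", that is 500 × 0.8 / 2 = 200. The design effect does not. D = 1 + ρ(m − 1) with the stated m = 6-8 gives 1.05-1.07 at ICC 0.01 and 1.25-1.35 at 0.05. The stated 1.084 and 1.419 need m = 1 + 0.084/0.01 = 9.4 and 1 + 0.419/0.05 = 9.38. The detectable difference (1.960 + 0.842)√(2D/200) from the stated D is 0.292-0.334 SD, against the stated 0.28-0.32. These are separate discrepancies. What matters here is that D has no advisor term.

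**2. Caseload.** The programme schedule runs 24 weeks and the manual calls it six months, so 12-18 months holds 2-3 rounds. If advisors repeat rounds (an assumption), each takes 5 × 2 = 10 to 7 × 3 = 21 clients, or 8 to 16.8 analysed after 20% attrition. That needs 250/21 ≈ 12 to 250/10 = 25 advisors for about 80/2 = 40 intervention towns, so some would have to cross towns. With one round each, 250/7 ≈ 36 to 250/5 = 50 advisors would serve, about one per town.

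**3. Error in the standard error.** Inputs:
- m_t = 200/40 = 5 analysed per town.
- Town ICC ρ_t = 0.01, the low end of the plan's power range.
- m_c = 8 to 16.8 analysed clients per advisor.
- Advisor ICC ρ_c = 0.01-0.05. This is assumed; the documents give none.
- Whole towns sit under one advisor.

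Formulas:
- Control-arm design effect: 1 + 4 × 0.01 = 1.04.
- Intervention arm as seen by town GEE: 1 + 4(0.01 + ρ_c).
- Intervention arm, true: 1.04 + (m_c − 1)ρ_c.
- Ratio of true to reported SE of the arm difference: R = √[(true + 1.04)/(seen + 1.04)].
- Real alpha = 2·P(Z > 1.960/R).

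Example, ρ_c = 0.02 and m_c = 16.8: true = 1.04 + 15.8 × 0.02 = 1.356; seen = 1.12; R = √(2.396/2.16) = 1.053; alpha = 6.3%.

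| Advisor ICC | Seen | True (m_c 8 to 16.8) | R | Real alpha, town GEE | Real alpha, unclustered test |
|---|---|---|---|---|---|
| 0.01 | 1.08 | 1.110-1.198 | 1.007-1.028 | 5.2-5.6% | 5.9-6.4% |
| 0.02 | 1.12 | 1.180-1.356 | 1.014-1.053 | 5.3-6.3% | 6.3-7.3% |
| 0.05 | 1.24 | 1.390-1.830 | 1.032-1.122 | 5.8-8.1% | 7.5-10.2% |

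The last column uses R = √[(true + 1.04)/2]. With no advisor effect it would already be 5.5% (R = √1.04), so part of it is the ignored town effect.

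**4. Limiting cases.** If each advisor serves one town, m_c = m_t = 5, true equals seen, and R = 1. A 20,000-replicate simulation of a town-robust GEE gave 5.1% for this case, against 5.3-5.5% with no advisor effect at all. With advisors assigned regardless of town and 10-20 clients each, simulated alpha was 6.6-7.3% at advisor ICC 0.02 and 8.0-10.9% at 0.05.

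**5. Power.** Replacing 2D by (true + 1.04), the detectable difference is 0.291 SD at best (true = 1.110) and 0.336 SD at worst (true = 1.830).

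**The case against.** The strongest objection is that the decisive facts are missing. A reader might infer that matching ignores town and that the error bars are therefore too narrow. The documents do not support that: the visit section gives no matching rule, which is silence, and the background describes coaches as living in the same community. If that means the same randomized town, town GEE already absorbs the advisor effect. This stands, and it makes the point conditional.

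A reader might also take the screening form's remark that the skills come more easily to some people as evidence that serving advisors differ. It describes candidates, and the same note says that some will not pass. Certification, scripted sessions with checklists and weekly supervision all reduce variation. The only empirical ICCs in the plan, 0.001-0.015 for most measures, are town-level and small. So the lower rows of the advisor ICC range deserve at least as much weight as 0.05.

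Counting 5-month rounds at full load over the whole study would give caseloads up to about 25 and an alpha near 10%. The six-month programme, prior training, 3-5 clients at a time and 20% attrition do not support that as a typical case.

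Finally, the inflation arises under a null of zero average effect with real differences between advisors, and with advisors treated as a random sample. If coaching changes nothing for anyone, there is no advisor variance to miss. That is an inferential choice, but a reasonable one for a programme presented as a model for other communities.

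What survives is that shared advisors in one arm are certain, crossing is likely, and the plan neither rules it out nor tests for it.

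**Conclusion.** The concern holds as a conditional gap. The documents establish multi-client advisors in the intervention arm only, and an analysis that allows for town at most. They do not establish that advisors cross towns or that outcomes differ by advisor, so it cannot be said that the standard error is too small, only that it can be.

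Under the stated assumptions the effect is modest. Alpha rises by at most about 0.6 percentage points at advisor ICC 0.01, 1.3 at 0.02 and 3.1 at 0.05. It is nil with one town per advisor. It is larger if advisors are assigned regardless of town or if the ICC threshold selects an unclustered test, although an advisor effect would itself raise the observed town ICC and make that selection less likely. This is worth settling in the analysis plan before unblinded analysis. It is not evidence that the trial's result would be wrong.

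**What to change.** - Record a peer advisor ID for each intervention participant. The participant workbooks and the initials on each session record already hold it. State the number of advisors, their total caseloads and the advisor-to-town assignment.
- Pre-specify a partially nested mixed model with a town random effect in both arms and an advisor random effect in the intervention arm only. Use a logistic version for adherence and a linear one for A1c, blood pressure and LDL-cholesterol.
- Fit it whatever the observed town ICC, and report it beside the town-level result. Otherwise it would not reach the primary test when the threshold selects a chi-square.
- Do not rely on GEE clusters formed from towns that share an advisor unless enough independent clusters remain and a small-sample correction is used. Overlapping caseloads can chain towns into very few clusters, where sandwich standard errors are themselves unreliable.

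The cost is analysis-plan wording and one variable the study already holds. The downside is somewhat wider intervals and an advisor variance that may be imprecise if advisors are few. If each advisor turns out to serve one town, the added term should change little.

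### For A1c, blood pressure, LDL and the secondary outcomes, the main test should be adjusted for baseline value and randomisation strata, not an unadjusted comparison of change scores

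*Combined protocol and SAP*

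**What the plan says.** The Data Analysis section names one primary analysis: binary medication adherence at follow-up, compared between arms by a chi-square test or a logistic GEE, unadjusted at first. This is a follow-up proportion, not a change score.

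A1c, blood pressure and LDL-cholesterol are also listed as primary outcomes. For these, and for the secondary outcomes, each participant's change from baseline to 6 months is computed: "These change scores will be the units of analysis and we hypothesize greater change among the intervention groups compared to the control group". The first comparison of changes is unadjusted (t-test, rank test, or GEE if clustering is judged non-negligible). Adjusted models follow in stages, "first adjusting for baseline values of outcome variables, then for any factors that were imbalanced at baseline", and finally for a listed covariate set that the section attributes to Table 6.

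The Randomization section stratifies the towns: "We will group towns by size (small and not small) within each of the 4 regions, resulting in 8 strata". Neither the power section nor the Data Analysis section mentions region, town size or strata. Clustering by town is handled by GEE or mixed models. No table numbered 6 is visible in the text, so its contents cannot be checked.

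**The concern.** A raw change score subtracts the whole baseline value, that is, it fixes the baseline slope at 1. When baseline and follow-up are imperfectly correlated this over-corrects, so the comparison is noisier than one that estimates the slope. It also carries part of any chance baseline difference into the estimated effect. The trial measures every baseline value it needs, so the lost precision could be recovered at no cost in data.

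Two smaller matters go with this. Strata used to allocate towns would normally be carried into the analysis. And imbalance is not defined, so one of the later models cannot be written down until the arms have been compared.

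The choice of governing model can also affect the result. Raw-change and baseline-adjusted estimates differ when the arms differ at baseline. Under the Randomization section the first enrollee fixes a town's arm and later residents join a town already allocated, so some baseline difference is possible.

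**Working it through.** **Inputs from the power section.** Two-sided alpha 0.05 and 80% power; "we assume 20% attrition here, leaving 200 participants per group" (500 x 0.8 = 400); "at least 80 clusters, corresponding to an average of 6-8 participants per cluster"; "we present power calculations for ICC=0.01-0.05"; design effect D of 1.084 and 1.419. Stated results: "Assuming 200 participants per group we will have 80% power using 2-sided t-tests to detect differences of 0.28-0.32 standard deviations for continuous outcomes", and "detectable differences for change in A1c are in a clinically meaningful range from 0.41-0.48" percentage points. The baseline to follow-up correlation r is not given; I assume 0.3 to 0.8.

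**Step 1: the plan's own figure.** Detectable difference = (1.960 + 0.842) x sqrt(2D/N), with N = 200.
- D = 1.084: 2.802 x sqrt(0.01084) = 0.292 SD (plan: 0.28).
- D = 1.419: 2.802 x sqrt(0.01419) = 0.334 SD (plan: 0.32).

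So the figures are not quite reproduced. Power at the stated differences is 76.7% and 76.6%, and about 218 per group would be needed for 80%. The stated D also implies about 9.4 participants per town (1 + 0.084/0.01 = 9.4; 1 + 0.419/0.05 = 9.38) rather than 6-8. That mismatch is a separate matter. The adjustment below multiplies whatever starting value is used, so I apply it to the printed A1c figures.

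**Step 2: baseline adjustment against raw change.** With common variance s² at both visits:
- change-score variance = 2s²(1 - r)
- baseline-adjusted variance = s²(1 - r²)
- ratio = (1 - r²)/[2(1 - r)] = (1 + r)/2

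The detectable difference is multiplied by sqrt((1 + r)/2).

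| r (assumed) | Variance ratio | Multiplier | A1c, from 0.41-0.48 | Extra participants raw change needs | Power, if 80% on raw change |
|---|---|---|---|---|---|
| 0.3 | 0.65 | 0.806 | 0.33-0.39 | 54% | 93.5% |
| 0.5 | 0.75 | 0.866 | 0.36-0.42 | 33% | 89.9% |
| 0.7 | 0.85 | 0.922 | 0.38-0.44 | 18% | 86.0% |
| 0.8 | 0.90 | 0.949 | 0.39-0.46 | 11% | 84.0% |

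The fifth column is 1/ratio - 1. Applied to the recomputed 0.292 and 0.334 SD, r = 0.8 gives 0.277 and 0.317. Even the least favourable row therefore brings the recomputed values just inside the plan's stated 0.28 and 0.32.

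If the two variances differ (s0 at baseline, s1 at follow-up), the change-score variance exceeds the adjusted variance by (s0 - r s1)². That is never negative, so adjustment does not lose precision in large samples; only the size of the gain changes.

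**Step 3: strata.** Suppose region and town size explain a share f of the between-town variance. D = 1 + ICC(m - 1) then becomes (1 - ICC) + m x ICC x (1 - f), and the detectable difference is multiplied by the square root of the ratio.
- ICC 0.05, m = 6.25, f = 0.10: 1.231/1.262, multiplier 0.988 (about 1% smaller).
- ICC 0.05, m = 9.375, f = 0.50: 1.184/1.419, multiplier 0.914 (about 9% smaller).
- ICC 0.01, m = 9.375, f = 0.25 and 0.50: multipliers 0.989 and 0.978 (about 1-2% smaller).

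The share f is an assumption; the documents give nothing on it.

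**The case against.** The strongest reply is that nothing here is invalid. Under randomisation an unadjusted change-score comparison is not biased for lack of adjustment, and it matches the power section, which is written for differences in mean change. Baseline adjustment is already planned, and regressing change on arm and baseline gives the same arm coefficient as regressing the 6-month value on arm and baseline. Strata apart, the model proposed here is in the plan already, and the dispute is over which result is the main one. All of this stands. The point concerns efficiency and naming the governing analysis.

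The magnitude rests on an unstated r, and on equal variances and the same correlation within and between towns. This also stands, and is why a range is shown. The strata gain may well be slight: the power section reports ICCs of 0.001-0.015 for most measures in the earlier trial, and differencing already cancels stable regional differences in level.

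Several stronger readings are tempting but not supported:
- **That the primary analysis is a change score.** It is binary adherence at follow-up. The (1+r)/2 result does not apply to it, and baseline adherence status could add nothing there because everyone enters non-adherent.
- **That the plan leaves covariates to observed imbalance.** The first test is unadjusted, so imbalance cannot alter it. The imbalance rule governs later models only, alongside the Table 6 set.
- **That strata are never used.** The visible text supports only that no described model contains them. Table 6 would in any case enter at the last stage.
- **That the baseline Morisky item count is ignored and would predict follow-up adherence.** The secondary analysis of continuous adherence follows the change-score approach, including its baseline-adjusted stage. The count's prognostic value is plausible but has no source in the documents.

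**Conclusion.** The point holds for the continuous outcomes. The main test for A1c, blood pressure, LDL and the secondary outcomes is the less precise of two analyses the plan already intends to run. Under equal variances, making the baseline-adjusted one the main test would cut variance by 10% (r = 0.8) to 35% (r = 0.3), with r assumed throughout. Some gain remains for any r below 1. Adding region and town size is worth about 1-2% of the detectable difference at ICC 0.01, and approaches 9% only at ICC 0.05 with half the between-town variance explained. The imbalance rule makes one set of later models depend on the data, but not the main test. For the primary binary outcome the only established gap is that the strata are absent from the described models; no gain has been quantified there.

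**What to change.** - **Continuous outcomes.** Name as the main analysis a town-clustered model of the 6-month value on arm, baseline value, region and town size. Keep the unadjusted change-score test as supporting.
- **Covariates.** Replace the imbalance rule with a pre-specified list, and state whether Table 6 includes region and town size.
- **Binary adherence.** Add region and town size to the logistic GEE. The baseline Morisky count is optional. Because the odds ratio becomes conditional on the covariates, report a marginal risk difference beside it.

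The cost is mainly wording, since the baseline values are collected and the strata are defined at randomisation. Three details need settling. The Randomization section gives no cut-off for a small town. It counts four regions where the Figure 3 caption names three. It also requires only three towns per stratum, so main effects for region and size (four parameters) are safer than eight stratum indicators.

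A small downside is sparse events in the adherence model. On the plan's illustration of 20% against 8.8-10.1% with 200 per arm, there would be 40 + 18 to 40 + 20, or about 58-60 adherent participants, for five parameters (arm, three region terms, size), or six with the Morisky count. A simpler fallback model should be stated in advance.
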